Choice of the non-inferiority design will enable the deliverance of substantial evidence to change clinical practice if the prevention of PJI with a single dose of prophylactic antibiotic is “no less effective than” antibiotic practices of longer duration (i.e., multiple doses). Members of the Danish orthopedic community have been involved in deciding the potentially increased serious infection rate difference, we are willing to tolerate. Because the sample size is based on the standard flow of THA within the Danish real-world setting, we did not conduct formal power or sample size calculations. Initially, we defined “appreciably worse” serious infection rates and the chances of an erroneously significant result, that is, a false positive, that the medical community will tolerate. The PJI rate in Denmark is between 0.5% and up to 5,1%, (mean 1,2%; 95% CI: 1,0-1,4) varying at departmental level (21). It was decided that we will be willing to tolerate a potentially increased serious infection risk difference of up to 0.1% (1‰ more having a PJI i.e., up to one per thousand).

Confidence intervals and p-values

All 95% confidence intervals (95%CIs) and *P*-values will be two sided. We will not apply explicit adjustments for multiplicity, rather we will interpret the key secondary endpoints with caution.

Primary endpoint: If we assume that the PJI risk is similar in the two groups (with 10,000 patients in each) we expect to achieve a precision (narrowness) in the two-sided 95% confidence intervals around the Odds Ratio (OR=1.000) from a Generalized Linear Mixed Model (GLMM), with 95% limits from 0.756 to 1.323; with a Random Effects factor for the 36 individual centers, and Fixed Effect factors for group, period and the interaction between group and period (Group \times Period). This was validated through multiple simulations. The same simulations were carried out with a population of 8,000 in each group for sensitivity, resulting in 95 % limits around the Odds Ratio (OR=1.000) from 0.731 to 1.368. Based on the CIs from these simulations, that

have very little variability, and the clinical importance of PJIs, a pragmatic non-inferiority margin should be chosen. Thus, non-inferiority will be shown if the upper limit of the two-sided 95% confidence interval for the odds ratio (derived from the GLMM) is less than 1.4 for the single dose as compared with the multiple doses group.

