The primary analyses will be based on the Intention to Treat (ITT) population, i.e., all patients undergoing the prespecified surgery corresponding to the specific year (cross-over, cluster randomization). Two-sided 95% confidence intervals will be estimated and reported enabling (standard) superiority interpretations. The primary statistical analysis model will be based on a *Generalized Linear Mixed Model*, with a random effects factor applied indexing the clinical center (36 levels: 1, 2, 3, ..., up to 36), a fixed effect will be applied for period (2 levels: 1st and 2nd year, respectively), and antibiotics group (2 levels: Single-dose and Multiple-dose, respectively), as well as the interaction between the two period and antibiotics group (period×group; 4 levels: 2×2 levels). For the primary endpoint: Noninferiority will be shown if the upper limit of the two-sided 95% CI for the odds ratio is less than 1.4 for the single antibiotic doses as compared with multiple doses.

In addition, subgroup analyses will be performed to examine the following known and suspected baseline risk factors for PJI infection will be compared: age (≥ 65 versus < 65 years), sex (male versus female), Anthropometric categories (BMI: ≥ 30 versus $< 30 \text{ kg/m}^2$) as well as morbid obesity (BMI: ≥ 40), and presence of diabetes (with versus without). Additional analyses of the study will assess whether the difference of PJI risk in the two treatment arms differ in specific subsets of patients: femoral stem cementation (antibiotic-loaded bone cement versus bone cement with no antibiotic-load and cementless fixation vs fixation with bone cement) and type of antibiotic (beta-lactam antibiotics versus other). The rationale for these analyses is that we suspect the risk of infection to be different in these subgroups. The pharmacokinetics of the antibiotics might have an impact on the infection rates in the relevant groups. The statistical approach for this evaluation of potential effect modifiers is a test for statistical interaction to evaluate whether the treatment effect varies across levels of the effect modifier (46).

Finally, blinded results from the statistical analyses (single-dose compared to multiple-dose) will be presented to the author group followed by development of two written interpretations. The author group will sign a consensus statement comprising both interpretations prior to the unsealing of the randomization code.(47)

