Missing data and sensitivity analyses

The main analyses will be based on the data as it appears in the database. Consequently, missing data is handled according to a Missing Completely At Random (MCAR) assumption (48). Conducting sensitivity analyses in a randomized trial assessing the risk of PJs following a single-dose versus multiple-dose antibiotic prophylaxis is essential to ensure the robustness and credibility of the findings. To evaluate the consistency of the primary endpoint and some or all the key secondary endpoints across various assumptions, missing data will be imputed using best-case, worst-case, best-worst-case, and worst-best-case imputations (49, 50) the results will be combined using Rubin's rule.

Additional analyses

Stratified analysis

In secondary analyses, important contextual factors for a binary endpoint will be examined using statistical interaction tests, as proposed by Christensen et al. (46). Known and suspected baseline risk factors for PJI will be evaluated as potential effect modifiers: age group (<65 vs \geq 65 years), sex (male vs female), anthropometric category (BMI: <30 vs \geq 30 vs $>$ 35 kg/m²) and presence of diabetes (with vs without). Additional analyses of the study will assess whether the difference of PJI risk in the two treatment arms differ in specific subsets of patients: femoral stem cementation (antibiotic-loaded bone cement vs bone cement with no antibiotic-load and cementless fixation vs fixation with bone cement) and type of antibiotic (beta-lactam antibiotics vs other). The rationale for these analyses is that we suspect the risk of infection to be different in these subgroups. The pharmacokinetics of the antibiotics might have an impact on the infection rates in the relevant groups. The statistical approach for this evaluation of potential effect modifiers is a test for statistical interaction to evaluate whether the treatment effect varies across levels of the effect modifier (46). The subgroup analyses will be presented as demonstrated in Mock-up Figure 3A and B. No additional analyses on the primary and key secondary outcomes are planned from baseline to 90-day follow-up.

Harms

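### The best/worst-case imputations are the only planned check on the MCAR analysis, and they offer nothing between scenarios that cannot challenge non-inferiority and one extreme bound

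*SAP*

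**What the plan says.** Under Missing data and sensitivity analyses, the main analysis uses the data as they stand in the database, so that "missing data is handled according to a Missing Completely At Random (MCAR) assumption". The same section treats sensitivity analysis as essential to robust and credible findings. For the primary endpoint and some or all key secondary endpoints it states that "missing data will be imputed using best-case, worst-case, best-worst-case, and worst-best-case imputations", and that "the results will be combined using Rubin's rule". It does not define the scenarios by arm, give an expected missing fraction, or say which scenario bears on the margin. Under Stratified analysis, further analyses of the primary and key secondary outcomes to 90 days are ruled out.

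The decision rule is under Analysis methods: "Noninferiority will be shown if the upper limit of the two-sided 95% CI for the odds ratio is less than 1.4", for single dose against multiple doses. Under Sample size and power calculation the national PJI rate is given as "mean 1,2%; 95% CI: 1,0-1,4) varying at departmental level". Under Confidence intervals and p-values, equal risks with 10,000 per group are expected to give an odds ratio of 1.000 "with 95% limits from 0.756 to 1.323", and 8,000 per group limits of 0.731 to 1.368.

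**The concern.** In a superiority trial, adding the same events to both arms usually works against the claim, because it dilutes the difference. In a non-inferiority trial dilution works for the claim. A scenario called worst-case can therefore look reassuring when it is the more lenient one. The one scenario that does press on the claim gives every missing single-dose patient a PJI risk of 100% against a background near 1.2%, about 83 times as high (100/1.2). The plan has no step between the two. If some outcomes are missing, a reader who wants to know whether non-inferiority survives a plausible excess of PJI among missing single-dose patients gets no answer.

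**Working it through.** **Inputs (all SAP).** 10,000 per arm; PJI rate 1.2%; margin 1.4 on the upper two-sided 95% limit; stated limits 0.756–1.323 and 0.731–1.368. The number missing is an assumption, because the SAP gives none.

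**Formula.** With a and b events among n per arm, SE of log OR = √(1/a + 1/(n−a) + 1/b + 1/(n−b)), and limits = OR × exp(±1.96 SE). Centre and period effects are ignored.

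**1. Reproducing the SAP's figures.** 99 vs 99 of 10,000: SE = √(2/99 + 2/9,901) = 0.1428, limits 0.756–1.323. 79 vs 79 of 8,000: 0.731–1.368. Both match, and both imply a rate of about 0.99%. At 1.2% (120 vs 120) the limits are 0.775–1.290. Results below cover 1.0% and 1.2%.

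**2. Scenarios, as the names are naturally read.** Best-case: no missing patient has PJI. Worst-case: all do, in both arms. Best-worst: only those on multiple doses do. Worst-best: only those on single dose do.

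**3. Equal worst-case.** Observed 135 vs 120: OR 1.127, upper limit 1.443. Adding 20 events per arm (0.2% missing) gives 155 vs 140: OR 1.109, upper limit 1.396. Adding 50 (0.5%) gives 185 vs 170: OR 1.090, upper limit 1.345. The estimate falls and the interval narrows because imputed events count as observed. The direction does not depend on this example. In simulations at a true OR of 1.4 and a 1.0% rate, the share of upper limits below 1.4 rises from 2.5% with none missing to 3.5% at 0.1% missing and 10.5% at 0.5%, if this scenario is read alone.

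**4. Best-case and best-worst.** Best-case leaves the upper limit almost unchanged (1.321 to 1.323 at a 1.0% rate with 1% missing). Best-worst moves towards single dose: 120 vs 140 gives OR 0.855, upper limit 1.093.

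**5. Worst-best.** From 120 vs 120, 130 vs 120 gives 1.392 and 131 vs 120 gives 1.402, so 11 missing single-dose patients cross the margin. From 99 vs 99, 105 vs 99 gives 1.399 and 106 vs 99 gives 1.411, so 7 do.

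| Observed OR | Missing per 10,000 to reach 1.4, rate 1.0% | Rate 1.2% |
|---|---|---|
| 1.0 | 7 | 11 |
| 0.9 | 17 | 23 |
| 0.8 | 27 | 35 |

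At 0.99% the first column is 7, 16 and 26. With 8,000 per arm and OR 1 the count is 3 at 1.0% and 6 at 1.2%.

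**6. The gap between.** Take 50 missing per arm, 120 vs 120 observed, and tenfold PJI odds in missing single-dose patients: odds 0.012/0.988 = 0.01215, times 10 = 0.1215, risk 0.1215/1.1215 = 0.108. Expected imputed PJIs are 50 × 0.108 = 5.4, against 50 × 0.012 = 0.6 on multiple doses. 125.4 vs 120.6 gives an upper limit of about 1.34. Worst-best on the same data (170 vs 120) gives 1.80. The plan shows only the second.

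**7. Pooling as written.** For 135 vs 120 with 20 missing per arm, the four log ORs average to an OR of 1.118. Mean within-scenario variance is 0.01487 and between-scenario variance 0.01468. Total = 0.01487 + 1.25 × 0.01468 = 0.0332. The upper limit is 1.60 with a normal quantile and 1.68 with Rubin's t. The width reflects the spread between four chosen extremes, not uncertainty about the missing values.

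**The case against.** The strongest reply is that none of this touches the decision. The 1.4 rule belongs to the main mixed-model analysis of the data in the database, and the imputations only examine consistency. That stands. A reader might infer from step 3 that a failed trial could be turned into a pass, or that the trial's type I error is inflated. The SAP does not support this: no sensitivity scenario replaces the primary result, and pooling as written gives an upper limit of about 1.6 to 1.7 in that example, wider than the observed 1.443.

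Second, the four scenarios form a bounding set, and worst-best belongs to it. That also stands. A reader might conclude that the set says nothing about robustness. It does say something: if non-inferiority survives worst-best, no pattern of missing outcomes could overturn it. The weakness is that failing it is uninformative once more than a few patients are missing.

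Third, missingness may be negligible. Under Outcome definitions and endpoints the SAP describes registry linkage with complete individual follow-up, and a patient with no recorded revision is ordinarily a non-event. One missing patient per arm moves 1.443 only to 1.440. This limits the practical effect. The SAP nevertheless plans to report loss to follow-up with reasons and to impute, and worst-best can become decisive at very small counts.

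Fourth, the by-arm meaning of the scenarios is inferred. It is the natural reading beside two opposing scenarios, and the text should state it.

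**Conclusion.** The point holds as a minor weakness in a supportive analysis. Three of the four scenarios leave the non-inferiority claim unchanged or favour it. The fourth is a legitimate outer bound that crosses 1.4 at about 7 to 11 missing single-dose patients per 10,000 when the observed odds ratio is 1, and at about 17 to 35 when it is 0.8 to 0.9. Pooling the four by Rubin's rule does not repair this, because deterministic scenarios are not draws from an imputation model. The figures rest on PJI rates of 1.0–1.2%, a simple two-by-two interval that reproduces the SAP's stated limits at 0.99%, and the inferred scenario definitions. The primary decision is not affected, and how much the weakness matters depends on a missing fraction that the SAP does not give and that may be very low.

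**What to change.** For the primary endpoint, add a tipping-point analysis. Multiply impute missing outcomes from the primary model with PJI odds in the single-dose arm raised in steps (for example ×1, ×2, ×5, ×10), and apply Rubin's rules only across the imputations within each step. Report the multiplier, and the number of extra single-dose PJIs, at which the upper limit reaches 1.4, together with the number missing per arm.

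Define the four scenarios by arm. Report worst-best separately as a labelled outer bound. Do not cite equal worst-case or best-case as evidence of robustness, and remove the pooling of the deterministic scenarios.

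The cost is a few sentences in the SAP and a short extra script, with no new data.

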Outcome	Single-dose (N =)	Multiple- dose (N =)	Odds Ratio (95% CI)	†Absolute risk difference (95%CI)
Primary Outcome				
Prosthetic Joint infection at 90 days, no. (%)				
Key Secondary Outcomes				
Serious adverse events (SAE), no. (%)				
PJI-likely, no. (%)				
Major Adverse Cardiovascular Events, no. (%)				
Length of stay (LOS), days				
Hospital-treated infections (excluding SSI), no. (%)				
Community-based antibiotic use, no. (%)				
Opioid use, no. (%)				
Use of acetaminophen/non-steroidal anti-inflammatory drugs , no. (%)				
Revision due to any cause, no. (%)				

* The primary analyses will be based on the Intention to Treat (ITT) population based on the Full Analysis Set; i.e., all patients undergoing the prespecified surgery using the antibiotic dose corresponding to the specific year (cross-over, cluster randomization). Two-sided 95% confidence intervals will be estimated and reported enabling (standard) superiority interpretations. The primary statistical analysis model will be based on a *Generalized Linear Mixed Model*, with a random effects factor applied indexing the clinical center (36 levels: 1, 2, 3, ..., up to 36), a fixed effect will be applied for period (2 levels: 1st and 2nd year, respectively), and antibiotics group (2 levels: Single-dose and Multiple-dose, respectively), as well as the interaction between the two (period×group; 4 levels: 2×2 levels). Hierarchical models account for variations in baseline risk across clusters (e.g., sites or patient subgroups). †Absolute risk differences and their 95% confidence intervals will be derived from odds ratios and corresponding 95% confidence intervals estimated by the hierarchical model, incorporating the baseline risk in the reference group (multiple-dose). The 95% confidence intervals will not be adjusted for multiplicity and should not be used in place of hypothesis testing.

Table 3. Serious Adverse Events within 90 days within each group. *

Events	Single-dose (N =)	Multiple-dose (N =)	Odds ratio (95% CI)	Absolute risk difference [†]
Serious adverse event — no. (%)				
Any infection requiring intravenous antibiotics				
Severe allergic reaction				
Organ failure				
Life-threatening events				
Musculoskeletal				
Deep infection				
Hip dislocation				
Femoral fracture				
Aseptic loosening				
Cardiovascular				
Vascular injury				
Pulmonary embolism				
Deep venous thrombosis				
Acute myocardial infarction				
Stroke				
Nervous system				
Nerve injury				
Death (All-cause mortality)				
Discontinuation due to adverse event(s) — no. (%)				
Discontinuation due to serious adverse event(s) — no. (%)				

* This table includes all serious adverse events that occurred during the 3month study period, but which did not necessarily have a causal relationship with the treatment administered. An adverse event was classified as serious if it was fatal or life-threatening, required or prolonged inpatient hospitalization, was disabling, resulted in (a congenital anomaly or birth defect), or required medical or surgical intervention to prevent permanent impairment or damage.

[†] Absolute risk (single-dose vs. Multiple-dose group) will also be calculated. The 95% confidence intervals will not be adjusted for multiplicity.

[figure not shown]
FIGURE 1: CONSORT flow-chart.

Figure 2. Kaplan Meier Curve. The cumulative proportion of patients remaining PJI-free in the two groups.

[figure not shown]
[figure not shown]
[figure not shown]

Figure 3 Subgroup analyses of the Primary Outcome in the Intention-to-Treat population. The primary outcome is prosthetic joint infection within 90 days after surgery. The reference group consists of patients assigned to the single-dose group. The confidence intervals for subgroup analyses are not planned to be adjusted for multiplicity and should not be used to infer definitive conclusions about treatment effects. The body-mass index is the weight in kilograms divided by the square of the height in meters. Additional analyses of the risk of PJI 90 days after surgery will assess whether the difference of PJI risk in the two treatment arms differ in specific subsets of patients: femoral stem cementation (antibiotic-loaded bone cement versus bone cement with no antibiotic-load versus cementless fixation) and type of antibiotic (beta-lactam antibiotics versus other). The reference group is patients assigned to single-dose. The rationale for these analyses is that we suspect the risk of infection to be different in these subgroups.

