The senior biostatistician was responsible for the randomization process. Each center was allocated based on a code provided by the senior biostatistician responsible and reported to a central database. The randomization and allocation procedure will be known for the given year. To minimize the risk of protocol violations, the steering committee—comprising the study coordinator JSL, the principal investigator AAA, and the sponsor SO, conducted meetings with all departments before the recruitment of the first patient and again after the first year to ensure effective implementation of the cross-over. Local study coordinators have been assigned at each study site prior to study start. The local study investigators consist of a team of an orthopedic surgeon or anesthesiologist and a nurse. The team was responsible for change of the standardized departmental instructions for antibiotic prophylaxis according to randomization, prior to study start. Furthermore, they have been responsible for organization and thorough information of all relevant personnel at the respective study sites. Relevant material has been developed and organized by the authors and distributed to the local study coordinators. Meetings were held in the summer and autumn of 2022. New meetings were done one year later before the cross-over of treatment was planned. Furthermore, any protocol deviations or violations which could occur was reported by the local investigators to the principal investigator and sponsor at 6-month evaluations.

The ITT principle was implemented for all participants allocated to a treatment group ($X_{\text{Single-dose}}$ and $X_{\text{Multiple-dose}}$, respectively). All participants will be followed up, assessed, and analyzed as members of that group. This approach ensures that the results reflect real-world clinical scenarios and maintains the integrity of the randomized design. The study was blinded for the statistical analyst TH but not the patients, investigators, nor departments.

Sample size and power calculation

Based on existing Danish national statistics, we anticipated that we will be able to include app. 20,000 eligible individuals having a THA when enrolling consecutively across 36 clinical centers over the two-year period; i.e., that would potentially enable a pragmatic intention-to-treat (ITT) population of up to 10,000 patients in each group (i.e., up to 10,000 individuals exposed to a single-dose antibiotics only).

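### The Table 2 rule turns odds-ratio limits into risk-difference limits as if the multiple-dose risk were known, so the reported intervals are mis-sized away from OR 1

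*SAP*

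**What the plan says.** Table 2 of the SAP has an odds-ratio column and an absolute risk-difference column, each with a 95% interval, for the primary outcome and the key secondary outcomes. The dagger footnote gives the rule for the second column: "Absolute risk differences and their 95% confidence intervals will be derived from odds ratios and corresponding 95% confidence intervals estimated by the hierarchical model". On where the baseline comes from, it says that the conversion is made by "incorporating the baseline risk in the reference group (multiple-dose" arm. It names three inputs: the odds ratio, its limits and a baseline risk. It gives no variance for that risk, no covariance with the odds ratio, and no delta method, standardisation or bootstrap.

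Under Analysis methods the SAP says: "Two-sided 95% confidence intervals will be estimated and reported enabling (standard) superiority interpretations". Non-inferiority is judged on the odds ratio alone, by whether its upper limit is below 1.4. Under Sample size and power calculation, the harm that the orthopaedic community would accept is put on the absolute scale: the trialists are "willing to tolerate a potentially increased serious infection risk difference of up to 0.1" per cent.

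**The concern.** The multiple-dose risk is estimated from the same trial as the odds ratio, so it has sampling error of its own. The two estimates are also negatively correlated: a chance excess of infections in the multiple-dose arm raises the baseline risk and lowers the odds ratio. An interval that moves only the odds ratio and holds the baseline at its observed value carries neither feature. At OR 1 the omissions cancel, so a check at the null shows nothing wrong. Away from the null they do not cancel.

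At stake is whether the absolute intervals in the main results table have their stated 95% coverage. Readers are likely to look at that column, because the tolerance of 0.1% is given on that scale. For PJI the mis-sizing depends on the result: false precision if single dose looks better, and excess width if it looks worse.

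**Working it through.** **Inputs from the SAP**
- Patients: "intention-to-treat (ITT) population of up to 10,000 patients in each group" (Sample size and power calculation), so n = 10,000 per arm.
- Baseline PJI risk: "The PJI rate in Denmark is between 0.5% and up to 5,1%, (mean 1,2%; 95% CI: 1,0-1,4" (same section), so p0 = 1.2%.
- Two-sided 95% intervals, z = 1.96.
- Expected precision of the odds ratio at OR 1: "with 95% limits from 0.756 to 1.323" for 10,000 per arm, and for 8,000 per arm "resulting in 95 % limits around the Odds Ratio (OR=1.000) from 0.731 to 1.368" (Confidence intervals and p-values). The SAP states no risk-difference interval.

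**Step 1: reproduce the stated odds-ratio limits.** Use exp(±1.96 × sqrt(2/(n p(1−p)))).
- p = 1.0%: 0.757 to 1.321 for n = 10,000, and 0.732 to 1.365 for n = 8,000. Both agree closely with the SAP.
- p = 1.2%: 0.775 to 1.290 and 0.752 to 1.329.

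The stated precision therefore corresponds to a risk of about 1.0%, the lower end of the SAP's interval for the mean. Coverage at 1.0% is nearly identical to that at 1.2%, so the choice does not affect what follows.

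**Step 2: compare the two variances.** Write v = p(1−p), with subscript 0 for multiple dose and 1 for single dose.
- Variance of the log odds ratio: (1/v1 + 1/v0)/n.
- With p0 held fixed, the risk difference changes by v1 per unit of log odds ratio. The plug-in variance is therefore v1² (1/v1 + 1/v0)/n = (v1 + v1²/v0)/n.
- Correct variance of p1 − p0: (v1 + v0)/n.
- Ratio of variances: v1/v0. Ratio of standard errors: sqrt(v1/v0), about sqrt(OR) for a rare outcome.

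Example at OR 0.75 and p0 = 1.2%: p1 = 0.009/(0.988 + 0.009) = 0.903%, v1 = 0.00895, v0 = 0.01186, and the ratio is sqrt(0.00895/0.01186) = 0.87.

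**Step 3: convert the limits.** An odds-ratio limit o becomes o·p0/(1 − p0 + o·p0) − p0. The direct interval is (p1 − p0) ± 1.96 × sqrt((v1 + v0)/n). Values are in percentage points, at p0 = 1.2% and n = 10,000.

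| OR | Plug-in interval | Width | Direct interval | Width |
|---|---|---|---|---|
| 0.75 | −0.512 to −0.016 | 0.497 | −0.580 to −0.015 | 0.565 |
| 1.0 | −0.267 to 0.343 | 0.610 | −0.302 to 0.302 | 0.604 |
| 1.4 | 0.125 to 0.908 | 0.783 | 0.142 to 0.802 | 0.659 |

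**Step 4: coverage by simulation.** Independent binomials, p0 = 1.2%, n = 10,000 per arm, 300,000 replicates, no clustering.

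| OR | SE ratio | Coverage of nominal 95% plug-in interval |
|---|---|---|
| 0.6 | 0.78 | 87.1% |
| 0.75 | 0.87 | 91.1% |
| 0.9 | 0.95 | 93.8% |
| 1.0 | 1.00 | 95.1% |
| 1.1 | 1.05 | 96.1% |
| 1.25 | 1.12 | 97.2% |
| 1.4 | 1.18 | 98.0% |

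The direct interval covers about 95% in every row.

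**Step 5: with clustering.** The check was repeated with a random-intercept logistic model in a cluster-crossover layout: 36 centers, 278 patients per center-period and 1,200 replicates. The between-center SD of 0.5 on the logit scale is an assumption. Plug-in coverage was 86.3% at OR 0.6, 90.9% at 0.75, 94.9% at 1.0 and 97.8% at 1.4. The odds-ratio interval itself covered 95% to 96%, so the fault lies in the conversion and not in the model.

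**Step 6: common outcomes.** The SAP gives no rates for the secondary outcomes, so a range of baseline risks is needed. At 10%, coverage is 91.9% at OR 0.75 and 97.5% at OR 1.4. Near 50% the error almost vanishes (94.8% and 94.7%). At 70% it reverses: about 96% at OR 0.75 and 93.0% at OR 1.4.

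**The case against.** **Treating the baseline as fixed is an inference.** The footnote does not use that word. If the risk difference were meant conditionally on a known external baseline, the converted limits would keep the coverage of the odds-ratio interval. But the footnote takes the risk from the trial's own multiple-dose arm and offers no way to carry its error, so plug-in remains the natural reading.

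**No decision rests on this column.** Non-inferiority is read from the odds ratio, and the same footnote warns against using the intervals in place of hypothesis tests. This stands, and it limits the consequence to reporting.

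**The error is small where the trial expects to be.** The precision statement assumes similar risks in the two arms. For OR 0.9 to 1.1, coverage is 93.8% to 96.1%. This stands too.

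**The 0.1% tolerance is not made easier to meet.** A reader might infer that intervals that are too narrow would let single dose pass that threshold falsely. The SAP never compares a risk-difference limit with 0.1%, and the arithmetic points the other way. In 400,000 simulated trials per scenario at p0 = 1.2% (10,000 per arm, no clustering), the upper limit fell below 0.1% in these shares of trials:
- OR 0.8: 60.4% plug-in, 63.8% direct.
- OR 0.9: 27.9% plug-in, 30.8% direct.
- OR 1.0: 8.3% plug-in, 9.6% direct.

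Against that threshold the plug-in rule is slightly cautious.

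**The rule has one convenience.** The converted interval excludes 0 exactly when the odds-ratio interval excludes 1, so the two columns can never disagree about the null. That is true, but it does not give the risk-difference interval its stated coverage.

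**Conclusion.** The concern holds as a fault in a reported interval. As written, the rule gives risk-difference intervals for the primary and binary secondary outcomes that miss 95% coverage once the arms differ. For PJI the shortfall is about 4 percentage points at OR 0.75 and about 1 point at OR 0.9; the excess is about 1 point at OR 1.1 and 3 points at OR 1.4.

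Two stronger readings are tempting and should not be drawn. The first is that the interval is always too narrow when single dose does better and too wide when it does worse. That holds only below about 50% risk, and Table 2 includes opioid, analgesic and antibiotic use, for which the SAP states no rates. The second is that the non-inferiority conclusion is compromised. The test uses the odds ratio, whose interval kept its coverage in the clustered check.

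The figures assume conversion at the observed multiple-dose risk, 10,000 per arm and a PJI risk of 1.2%. They ignore clustering, except in the one check with an assumed between-center SD.

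**What to change.** Replace the footnote rule. Estimate each risk difference by marginal standardisation from the fitted mixed model: predict every patient's risk under each regimen, average over patients and over the distribution of the center random effect, and subtract. Take the 95% interval from the delta method on the full covariance matrix or from a bootstrap that resamples centers. Either carries the uncertainty in the baseline risk and its covariance with the odds ratio.

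The listed packages (lme4, emmeans) are a start, but default emmeans predictions set the center effect to zero and are not this average, so some extra code is needed.

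The cost is one sentence in the SAP and that code. In borderline cases the risk-difference interval may disagree with the odds-ratio interval about the null. The SAP should say in advance that the odds ratio governs inference.
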